- Immunogenicity, CCl and PK sampling to be performed at the indicated visits and prior to dose administration if the visit is a dosing visit. Samples will be taken in the event of early termination. Immunogenicity samples also may be collected in the event of a systemic allergic/hypersensitivity reaction (see Section 8.4.3). The timing of samples will be recorded.
- k Patients will receive injections of placebo or LY2951742 after all other visit procedures are completed. Following the first dose at Visit 3, patients will be observed for at least 30 minutes in the office.
- 1 Questionnaire administered by clinician to assess other chronic pain conditions.
- m The C-SSRS and SHSF (and SHFU when applicable) will be completed at scheduled and unscheduled office visits.

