5.5.1.5. Baseline and Post-Baseline Definition

Table 5.5 describes the rules for determining the patient population and baseline and post-baseline observations for each study phase and type of analysis. When "last of Visit x-x" is used in the table, the last nonmissing observation obtained in the visit interval will be used.

^{*}No subgroup analysis by region2 for CGAG since all patients will be from North America.

Table 5.5. Patient Population with Baseline and Post-Baseline Definitions by Study Period and Type of Analysis

Study Period/Analysis	Patient Population	Baseline Observation	Post-baseline Observation(s)
Study Period III			
Primary/secondary/exploratory efficacy analyses (repeated measures or average of observed monthly values)	ITT population with a baseline and at least one post-baseline observation	Visit 3	All scheduled visits 3 <visits<=12< td=""></visits<=12<>
Primary/secondary/exploratory efficacy analyses at LOCF endpoint	ITT population with a baseline and at least one post-baseline observation	Visit 3	Last of Visit 3.01- 12
Quality of Life analyses (repeated measures)	ITT population with a baseline and at least one post-baseline observation	Visit 3	All scheduled visits 3 <visits<=12< td=""></visits<=12<>
Quality of Life analyses at LOCF endpoint or for average of observed monthly values	ITT population with a baseline and at least one post-baseline observation	Visit 3	Last of Visit 3.01- 12
TEAEs	Safety population	All Visits 1-3	All Visits 3.01-12
Serious adverse events, discontinuations due to adverse events	Safety population	NA	All Visits 3.01-12
C-SSRS categorical analyses	Safety population with a baseline and at least one post-baseline C-SSRS assessment	Recent history: All Visits 1-3 excluding lifetime ^a All prior history: Visits 1-3 including lifetime ^a	All Visits 3.01-12
Treatment emergent abnormal laboratory values	Safety population with normal laboratory values at all nonmissing baseline visits (with respect to direction being analyzed) and who have at least one post-baseline observation	Low: Minimum value from Visits 1-3 High: Maximum value from Visits 1-3	Low: Minimum value from Visits 3.01-12 High: Maximum value from Visits 3.01-12
Treatment emergent immunogenicity	Safety population	Visit 3	All Visits 3.01-12

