5.5.12.1.2. Suicide-Related Thoughts and Behaviors

Suicidal ideation, suicidal behavior, and self-injurious behavior without suicidal intent occurring during treatment, based on the Columbia-Suicide Severity Rating Scale (C-SSRS), will be summarized by treatment. In particular, for each of the following events, the number and percent of patients with the event will be enumerated by treatment: completed suicide, nonfatal suicide attempt, interrupted attempt, aborted attempt, preparatory acts or behavior, active suicidal ideation with specific plan and intent, active suicidal ideation with some intent to act without

specific plan, active suicidal ideation with any methods (no plan) without intent to act, nonspecific active suicidal thoughts, wish to be dead, and self-injurious behavior without suicidal intent.

In addition, the number and percent of patients who experienced at least 1 of various composite measures during Study Period III and Study Period IV separately will be presented and compared. Composite measures include suicidal behavior (completed suicide, non-fatal suicidal attempts, interrupted attempts, aborted attempts, and preparatory acts or behavior), suicidal ideation [active suicidal ideation with specific plan and intent, active suicidal ideation with some intent to act without specific plan, active suicidal ideation with any methods (no plan) without intent to act, non-specific active suicidal thoughts, and wish to be dead], and suicidal ideation or behavior.

The number and percent of patients who experienced at least 1 of various comparative measures during treatment will be presented and compared for Study Period III and summarized for SP IV. Comparative measures include treatment emergent suicidal ideation compared to recent history, treatment emergent serious suicidal ideation compared to recent history, emergence of serious suicidal ideation compared to recent history, improvement in suicidal ideation at endpoint compared to baseline, and emergence of suicidal behavior compared to all prior history.

Specifically, the following outcomes are C-SSRS categories and have binary responses (yes/no). The categories have been re-ordered from the actual scale to facilitate the definitions of the composite and comparative endpoints, and to enable clarity in the presentation of the results.

Category 1 – Wish to be Dead

Category 2 – Non-specific Active Suicidal Thoughts

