Category 3 – Active Suicidal Ideation with Any Methods (Not Plan) without Intent to Act

Category 4 – Active Suicidal Ideation with Some Intent to Act, without Specific Plan

Category 5 – Active Suicidal Ideation with Specific Plan and Intent

Category 6 – Preparatory Acts or Behavior

Category 7 – Aborted Attempt

Category 8 – Interrupted Attempt

Category 9 – Actual Attempt (non-fatal)

Category 10 – Completed Suicide

Self-injurious behavior without suicidal intent is also a C-SSRS outcome (although not suicide-related) and has a binary response (yes/no).

Composite endpoints based on the above categories are defined below.

- Suicidal ideation: A "yes" answer at any time during treatment to any one of the five suicidal ideation questions (Categories 1-5) on the C-SSRS.
- Suicidal behavior: A "yes" answer at any time during treatment to any one of the five suicidal behavior questions (Categories 6-10) on the C-SSRS.

 Suicidal ideation or behavior: A "yes" answer at any time during treatment to any one of the ten suicidal ideation and behavior questions (Categories 1-10) on the C-SSRS.

The following outcome is a numerical score derived from the C-SSRS categories. The score is created at each assessment for each patient and is used for determining treatment emergence.

• Suicidal Ideation Score: The maximum suicidal ideation category (1-5 on the C-SSRS) present at the assessment. Assign a score of 0 if no ideation is present.

For Study Period III and Study Period IV, comparative endpoints of interest are defined below. "Treatment emergence" is used for outcomes that include events that first emerge or worsen. "Emergence" is used for outcomes that include events that first emerge.

- Treatment emergent suicidal ideation compared to recent history:
 An increase in the maximum suicidal ideation score during treatment (Visits 3.01 to 12 for SP III; Visits 12.01 to 14 for SP IV) from the maximum suicidal ideation category during the screening and lead-in periods (C-SSRS scales taken at Visits 1 to 3 excluding "lifetime" for SP III; C-SSRS scales taken at Visits 1 to 12.02 excluding "lifetime" for SP IV). Recent history excludes "lifetime" scores from the Baseline C-SSRS scale or Baseline/Screening C-SSRS scale.

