- Treatment-emergent serious suicidal ideation compared to recent history: An increase in the maximum suicidal ideation score to 4 or 5 on the C-SSRS during treatment (Visits 3.01 to 12 for SP III; Visits 12.01 to 14 for SP IV) from not having serious suicidal ideation (scores of 0-3) during the screening and leadin periods (C-SSRS scales taken at Visits 1-3 excluding "lifetime" for SP III; C-SSRS scales taken at Visits 1 to 12 excluding "lifetime" for SP IV). Recent history excludes "lifetime" scores from the Baseline C-SSRS scale or Baseline/Screening C-SSRS scale.
- Emergence of serious suicidal ideation compared to recent history:
 An increase in the maximum suicidal ideation score to 4 or 5 on the C-SSRS during treatment (Visits 3.01 to 12 for SP III; Visits 12.01 to 14 for SP IV) from no suicidal ideation (scores of 0) during the screening and lead-in periods (C-SSRS scales taken at Visits 1 to 3 excluding "lifetime" for SP III; C-SSRS scales taken at Visits 1 to 12 excluding "lifetime" for SP IV). Recent history excludes "lifetime" scores from the Baseline C-SSRS scale or Baseline/Screening C-SSRS scale.
- Improvement in suicidal ideation at endpoint compared to baseline: A decrease in suicidal ideation score at endpoint (the last measurement during treatment; Visits 3.01 to 12 for SP III; the last measurement during open-label phase Visits 12.01 to 14 for SP IV) from the baseline measurement (the measurement taken just prior to treatment Visit 3 for SP III; the last non-missing measure during Visits 3.01 to 12 for SP IV).

• Emergence of suicidal behavior compared to all prior history:
The occurrence of suicidal behavior (Categories 6-10) during treatment (Visits 3.01-12 for SP III; Visits 12.01 to 14 for SP IV) from not having suicidal behavior (Categories 6-10) prior to treatment (Visits 1-3 including "lifetime" for SP III; C-SSRS scales taken at Visits 1 to 12 including "lifetime" for SP IV).

Patients who discontinued from the study with no post-baseline C-SSRS value will be considered unevaluable for analyses of suicide-related events. Only evaluable patients will be considered in the analyses. Fisher's exact test will be used for treatment comparisons. For each event, p-values will only be displayed if at least 4 events occurred in at least 1 treatment group.

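### The suicidality table relies on C-SSRS answers alone, so a suicide, or a serious attempt with no return visit, can be dropped or scored as no event while the SAE table shows it

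*SAP*

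**What the plan says.** SAP 5.5.12.1.2 (Suicide-Related Thoughts and Behaviors) states that the suicide outcomes during treatment, "based on the Columbia-Suicide Severity Rating Scale (C-SSRS), will be summarized by treatment". The listed outcomes include "Category 10 – Completed Suicide" and non-fatal actual attempt (Category 9). The composite is defined as "Suicidal behavior: A 'yes' answer at any time during treatment to any one of the five suicidal behavior questions (Categories 6-10) on the C-SSRS".

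The same section restricts who is counted: "Patients who discontinued from the study with no post-baseline C-SSRS value will be considered unevaluable for analyses of suicide-related events", followed by "Only evaluable patients will be considered in the analyses". SAP Table 5.5 (Section 5.5.1.5) sets the matching Study Period III population for the C-SSRS categorical analyses: "Safety population with a baseline and at least one post-baseline C-SSRS assessment".

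On collection, a footnote to the protocol's Schedule of Activities (Appendix 2) says: "The C-SSRS and SHSF (and SHFU when applicable) will be completed at scheduled and unscheduled office visits". The schedule row marks the C-SSRS at Visits 1, 2, 3, 5, 6, 7, 8, 10, 12, 13 and 14 and at early termination. It is blank at Visit 4.

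Neither document brings SAE records, deaths or the self-harm forms into this analysis. Protocol 9.5.3 is also based on the C-SSRS.

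**The concern.** A form completed at an office visit needs a patient who comes to the office. The gravest outcome in the table, completed suicide, rules out a later visit by that patient, and a serious attempt makes one less certain. Missing data here therefore depend on the outcome being counted, and the loss runs in one direction, toward fewer events.

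Suicidality is a named safety endpoint, and protocol 8.2.1.2 says its assessment is required by a regulator. A reader of the suicidality table would take a zero to mean that no suicide or attempt occurred. Under the present rule it could also mean that one occurred and no form followed. The SAP plans no output that reconciles the two sources.

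**Working it through.** There is no plan figure to reproduce for this point. The check sets the rules side by side and follows a patient through them.

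**Step 1. First scheduled post-baseline form.** Baseline for Study Period III ends at Visit 3. Appendix 2 gives target intervals of 14 days from Visit 3 to Visit 4 and 16 days from Visit 4 to Visit 5. With no C-SSRS marked at Visit 4, the first scheduled post-baseline form is at 14 + 16 = 30 days (Visit 5), unless an unscheduled or early-termination visit comes first.

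**Step 2. Two cases for an event with no later C-SSRS.**

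| Situation | Evaluable? | Effect on the table |
|---|---|---|
| No post-baseline C-SSRS, e.g. event before Visit 5 | No | Removed from numerator and denominator |
| Earlier post-baseline forms, all answered no | Yes | Kept in the denominator as a non-event |

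Both results follow from the event definition and the evaluability rule as written.

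**Step 3. Is there a safety net inside the analysis?**
- The SAE row of Table 5.5 uses the safety population with no C-SSRS requirement, and protocol 8.2.1 requires SAEs to be reported within 24 hours of investigator awareness. The data therefore exist, but 5.5.12.1.2 does not draw on them.
- The deviation check for missing C-SSRS in Study Period III (SAP Appendix Table 1) applies to patients with a Visit 5 date and excuses patients lost to follow-up who have no post-baseline measures. A patient lost before Visit 5 is not flagged.
- For hypersensitivity, injection-site events and upper respiratory infections, the SAP identifies events from AE terms. Suicidality has no such step.

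**Step 4. Size, with assumed event counts.** The documents give no event rate. Arm sizes are the planned 206 per active arm and 413 on placebo (protocol 9.1). P-values are from the two-sided Fisher's exact test, the test the SAP names.
- One event in an active arm: 1/206 = 0.49%. It becomes 0/205 if the patient is excluded and 0/206 if the patient is scored as a non-event.
- Four events in one active arm against 0/413: 4/206 = 1.94%, p = 0.012.
- The same arm with one event lost: 3/205 = 1.46%, p = 0.036 (excluded), or 3/206 = 1.46%, p = 0.037 (scored as a non-event).

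The SAP shows a p-value only when some group has at least 4 events. In the four-event example, losing one event would also suppress the p-value. With 0 to 2 events per arm, no p-value would be shown either way, and the effect is on the count and percentage alone.

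**The case against.** The strongest reply is that the plan has several ways to catch these patients and that nothing is lost from safety reporting. Much of this stands.

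- **Attempt survivors.** Patients who stop early have early-termination procedures, which include a C-SSRS. They are then asked to enter Study Period IV, which has further forms at Visits 13 and 14. Unscheduled office visits also carry the form. A reader might infer that every serious attempt leading to withdrawal is missed; the documents do not support that. The gap concerns a patient who never comes back.
- **Other tables.** A suicide or serious attempt known to the site goes to the SAE output on the safety population, and an independent committee reviews safety data. A reader might infer that the trial could hide its whole suicide signal. It could not; only this analysis is affected.
- **Category 10.** A patient cannot answer an item on completed suicide, so the category presupposes that someone else records it, and a record made after a death would make the patient evaluable. That is reasonable, but neither document describes it, and the only stated setting for the form is the office visit. At the least, the SAP must say how Category 10 is populated.
- **Study Period IV.** It is tempting to add a 60-day gap from Visit 12 to Visit 13. That is one reading only: Table 5.5 has no C-SSRS row for Study Period IV, and the evaluability sentence does not say that baseline is reset for that period.

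**Conclusion.** The point holds for the suicidality table. As written, the rule can remove a known suicide, or a serious attempt with no return visit, from the counts or score it as no event. The error runs toward reassurance and can leave this table at odds with the SAE table. It affects the C-SSRS counts, percentages and Fisher tests, and not the SAE reporting.

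The likely size is one or a few events, which is material only because such events are expected to be few; that expectation and all event counts used here are assumptions. The conclusion also assumes that no one completes a C-SSRS on the patient's behalf after a death, since no such route is described. This is a cheap improvement, not a threat to the trial's safety conclusions.

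**What to change.** In SAP 5.5.12.1.2 and Table 5.5:

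1. Count any completed suicide or suicide attempt recorded as an SAE, including deaths, as a Category 10 or Category 9 event. Assign it by onset date to the study period, whether or not a C-SSRS exists.
2. Treat such patients as evaluable for the suicidal-behavior outcomes.
3. Count each event once when both sources record it, and footnote the source.
4. Keep the present evaluability rule for ideation outcomes and for patients with no event in either source.
5. Add the missing Study Period IV C-SSRS row to Table 5.5, stating its baseline and population.

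The cost is a short SAP edit and a match of SAE data already collected to the C-SSRS data, with a check for duplicates. The downside is that the behavior rows then mix two sources, which the footnote makes visible. The change should stop at suicides and attempts reported as SAEs. Extending it to other suicidal behavior in AE records would need a term list and a mapping to Categories 6 to 8. It would also be incomplete, because protocol 8.2.1.2 keeps nonserious events elicited through the questionnaire out of the AE record unless they lead to discontinuation.

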5.5.12.1.3. Vital Signs and Weight

Vital signs collected during the study include systolic and diastolic blood pressure, pulse, and temperature. Blood pressure and pulse measurements will be taken when the patient is in a sitting position. Three measurements of sitting blood pressure and pulse will be collected at approximately 30-60 second intervals at every visit and the 3 sitting blood pressure measurements and 3 pulse values will be averaged and used as the value for that visit.

The number and percent of patients meeting criteria for treatment-emergent abnormalities in vital signs and weight at any time during study will be summarized. Treatment group comparisons will be performed using Fisher's exact test. Table 5.7 displays the criteria used to define treatment emergent changes in vital signs and weight. The last column of the table displays the patient populations defined by baseline categories, the treatment-emergent categorical changes will be analyzed for each of those patient populations. The criteria generally consist of 2 parts, an absolute threshold and a change from baseline amount. The baseline and post-baseline definitions for vital signs analyses are in Table 5.5.

Table 5.7 displays the criteria for categorical changes of interest in vital signs and weight, The last column of the table displays the patient populations defined by baseline categories.

The criteria generally consist of 2 parts, an absolute threshold and a change from baseline amount.

- The absolute threshold in the criteria is based on 1) minimum post baseline when the direction is low; 2) maximum post baseline when the direction is high.
- The change from baseline amount in the criteria is 1) decrease from baseline (defined below and in Table 5.5) to minimum post baseline when the direction is low; 2) increase from baseline (defined below and in Table 5.5) to maximum post baseline when the direction is high.

The baseline for SBP, DBP, and pulse is defined as the last non-missing baseline value during the baseline period (see Table 5.5). To be exact,

• For analyses including double-blind treatment phase, the baseline for SBP, DBP, and pulse is defined as the last non-missing value before randomization. The rationale for using the last available value in the baseline period is to minimize the potential

- confound of discontinuing or dose stabilization of medications that modulate BP and pulse during the screening phase (which early in the baseline period).
- Similarly, for other study phases, the baseline is defined as the last non-missing value before patients enter the study phases of interest. The baseline definition was chosen to be consistent with the analysis approach for the double blind treatment phase as described above.

This baseline definition for SBP, DBP, and pulse applies to all analyses (both continuous and categorical) for SBP, DBP, and pulse.

The baseline and postbaseline values for temperature and weight are defined below (also in Table 5.5):

- For continuous analyses of temperature and weight, last nonmissing baseline during the baseline period will be used as the baseline.
- For the analyses of categorical changes of interest in temperature and weight,
 - o the baseline is defined as the minimum value during baseline period when the direction of change is low.
 - o the baseline is defined as the maximum value during baseline period when the direction of change is high.

Table 5.7. Criteria for Categorical Changes of interest in Vital Signs and Weight

Parameter	Direction	Criteria	Patients Population defined by Baseline Categories
Systolic BP (mm Hg)	Low	≤90 and decrease ≥20	All patients; >90; ≤90
(sitting)	High	≥140 and increase ≥20	All patients; <140, ≥140
	PCS High	≥180 and increase ≥20	All Patients;<180; ≥180
	Sustained Elevation	≥140 and increase ≥20 at 2 consecutive visits	All patients; <140; ≥140
Diastolic BP (mm Hg)	Low	≤50 and decrease ≥10	All patients; >50; ≤50
(sitting)	High	≥90 and increase ≥10	All patients; <90, ≥90
	PCS High	≥105 and increase ≥15	All Patients; <105; ≥105
	Sustained Elevation	≥90 and increase ≥10 at 2 consecutive visits	All patients; < 90; ≥90
Systolic BP or Diastolic BP (mm Hg) (sitting)	Sustained Elevation	Meeting criteria for systolic BP for 2 consecutive visits or meeting criteria for diastolic BP for 2 consecutive visits or both	All Patients
Pulse (bpm) (sitting)	Low	<50 and decrease ≥15	All patients; ≥50; <50
	High	>100 and increase ≥15	All patients; ≤100; >100
	Sustained Elevation	>100 and increase ≥15 at 2 consecutive visits	All patients; ≤100; >100
Weight (kg)	Low	(Loss) decrease ≥7%	All patients
	High	(Gain) increase ≥7%	All patients
Temperature (° F)	Low	<96° F and decrease ≥2° F	≥96°F
	High	≥101° F and increase ≥2° F	<101°F

Abbreviations: BP = blood pressure; bpm = beats per minute; F = degrees Fahrenheit; kg = kilograms; mm Hg = millimeters of mercury; PCS= Potentially Clinically Significant.

5.5.12.1.4. Electrocardiogram Intervals and Heart Rate

Analyses of corrected QT (QTc) interval will be calculated using 2 correction formulas. The QTcF (msec) will be calculated with Fridericia's formula as QT/RR $^{1/3}$. The Large Clinical Trial Population Based QT Correction (QTcLCTPB) (msec) will be calculated with the formula as QT/RR $^{0.413}$. For the QTc calculations, the unit for QT is milliseconds and the unit for RR is seconds. For patients with QRS \geq 120 milliseconds at any time during the study, the QT and QTc interval will be excluded from the analyses. A listing of ECG data for patients with QRS \geq 120 milliseconds at any time during the study will be provided.

The baseline for ECG is defined as the last non-missing baseline value during the baseline period (see Table 5.5). To be exact,

- For analyses including double-blind treatment phase, the baseline for ECG is defined as the last non-missing value before randomization. The rationale for using the last available value in the baseline period is to minimize the potential confound of discontinuing or dose stabilization of medications that modulate ECG during the screening phase (which is early in the baseline period).
- Similarly, for other study phases, the baseline is defined as the last non-missing value before patients enter the study phases of interest. This baseline definition was chosen to be consistent with the analysis approach for the double-blind treatment phase as described above.

This baseline definition for ECG applies to all analyses (both continuous and categorical, quantitative and qualitative) for ECG.

The baseline and postbaseline values are summarized in Table 5.5.

The number and percent of patients meeting criteria for treatment emergent abnormalities in ECG intervals (PR, QRS, QTcF, and QTcLCTPB) and heart rate at any time during study will be summarized. Treatment group comparisons will be performed using Fisher's exact test. Table 5.8 displays the criteria for treatment emergent changes in ECG intervals, heart rate and QTcLCTPB. For QTcLCTPB, the treatment-emergent low and high criteria are listed by gender and age range, based on Lilly reference ranges. The absolute threshold in the criteria is based on 1) minimum post baseline when the direction is low; 2) maximum post baseline when the direction is high.

- For Treatment emergent low analyses: Patients with all normal or high values at baseline (no low values) will be included.
- For Treatment emergent high analyses: Patients with all normal or low values at baseline (no high values) will be included.
- For Treatment emergent increase analyses: Patients with a baseline and at least 1 postbaseline result will be included.

The baseline and post-baseline values are summarized in Table 5.5.

Table 5.8. Criteria for Treatment Emergent Changes in ECG Intervals and Heart Rate

Parameter	Direction	Cri	teria
Heart Rate (bpm)	Low	<50 and d	ecrease ≥15
	High	>100 and increase ≥15	
PR Interval (msec)	Low	<	120
	High	≥′.	220
QRS Interval (msec)	Low	<	60
	High	>	120
QTcF (msec)	Low	Males: <330	Females: <340
	High	Males: >450	Females: >470
		>500	Omsec
	Increase	Increase	>30 msec
		Increase	>60 msec
		Increase	>75 msec
QTcLCTPB (msec)	Low	Male (All ages): <330;	Female (All ages): <340
	High	Male	Female
		Age (yrs): criteria	Age (yrs): criteria
		<18: >444	<18: >445
		18-25: >449	18-25: >455
		26-35: >438	26-35: >455
		36-45: >446	36-45: >459
		46-55: >452	46-55: >464
		56-65: >448	56-65: >469
		>65: >460	>65: >465
		>500 msec Increase >30 msec Increase >60 msec Increase >75 msec	
	Increase		

In addition, descriptive summary of qualitative ECG abnormalities will be conducted which will include summaries of 11 ECG categories (Axis, Rhythm, Conduction, Ischemia, Infarction, Injury, Morphology, U-waves, T-waves, ST Segment, and Other Abnormalities) of qualitative findings at any time post-baseline. A category is a collection of possible descriptions (findings) of one qualitative aspect of an ECG. A category name is the name of the qualitative aspect of the ECG (for example, Rhythm, Conduction, Morphology, Ischemia, and so forth). A finding is one of the possible specific descriptions (for example, Sinus Bradycardia, Acute Septal Infarction) within a category.

The summaries of the 11 ECG categories will exclude ECGs with any of the following: overall ECG could not be evaluated by the cardiologist, lead reversals or <9 leads, nonmatching demographic data, and those suggesting patient identification errors.

